10.4. Pass/fail criteria

There will be no formal success criteria for safety in this PMCF investigation.

The estimate rate (proportion) of hospital-acquired pressure injuries in hospital-admitted patients with a 95% confidence interval must be comparable to the confidence proportion and interval of the results found by Mölnlycke (5.3% [2.3%; 10.1%])³.

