10.1. Statistical design, method and analytical procedures

Definition of analysis populations

Safety populations and Intention to Treat (ITT) will be defined at a formal data review meeting before database lock. As a minimum, the data manager, the clinical manager and the statistician will be involved in the classification of subjects.

The safety population will be constituted by all subjects with valid informed consent. The ITT population (full analysis set) will be constituted by all subjects with valid informed consent, who have been exposed to the Test Product, with information on at least one endpoint.

The summary of the primary and secondary endpoints will be based upon the safety population, whereas the statistical analysis of the exploratory endpoint will be based on the ITT population. Invalid individual data points may be omitted from analysis even though the corresponding subject is part of the ITT population. Any exclusion of data points will be documented.

A formal per protocol (PP) population is not planned due to the explorative nature of the investigation. Considering the data obtained it might be considered to make additional explorative analyses based on a subset of the ITT population.

Analysis of the endpoints and baseline data.

The endpoints as well as baseline assessments will be listed and summarized by descriptive statistics. The summaries will be made for relevant visits (baseline or V1-V8), separately.

Summary statistics for continuous variables are presented with N, Mean, SD (standard deviation), Median, Min and Max, where N denotes the number of subjects contributing with non-missing data. For discrete variables, summary statistics are presented with N and percentage, where percentage is based on the total number of subjects/observations with non-missing data.

The incidence rate (proportion) of hospital-acquired pressure injuries in hospital-admitted patients will be estimated based on the exploratory endpoint (pressure injuries: Yes/No). The proportion of completed subjects answering "Yes" will be calculated. By use of an exact test in the Binomial distribution a 95% confidence interval will be estimated for the proportion.

All statistical analysis will be performed with SAS (version 9.4/Enterprise Guide version 7.1).

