10.2. Sample size

A sample size of 67 subjects will be enrolled with a minimum of 50 completers. This number is assessed to be sufficient to evaluate safety of the product.

The exploratory purpose of the investigation is to estimate the proportion of hospital-acquired pressure injuries in hospital-admitted patients with a 95% confidence interval. The confidence interval is then to be compared with the confidence interval of the results found by Mölnlycke. In the Mölnlycke investigation, the incidence in the control group was estimated to 5.3% [2.3%; 10.1%]³. 50 completing subjects will give a power of more than 80% to show an upper 95% confidence limit of 7.2% or less. This calculation assumes, that the true incidence rate for Biatain Silicone Sacral is 1.2% as we expect it to be as good as the intervention group in the Mölnlycke investigation³. It is further assumed that the confidence interval will be estimated as an exact confidence interval for binomial proportions. The precision of the estimated rate and the chosen sample size is evaluated to be sufficient to draw comparative conclusions between the rate of hospital-acquired sacral pressure injuries found in the suggested observational investigation and rates of hospital-acquired pressure injuries reported in literature.

To account for an estimated drop-out rate of 30%, 67 subjects must be enrolled to assure, that 50 subjects will complete the investigation.

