10.3. Level of significance and power

A two-sided significance level of 5% will be applied. For a description of the power see section 10.2 above.

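### The plan's only pass/fail rule asks for a pressure-injury rate comparable to a control-group rate, with no margin or direction, so meeting it cannot support preventive performance

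*Combined protocol and SAP*

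**What the plan says.** Section 10.4, headed as pass/fail criteria, first states that safety has no formal success criterion. It then requires that the estimated pressure-injury rate "with a 95% confidence interval must be comparable to the confidence proportion and interval of the results found by" the reference trial, quoted as 5.3% [2.3%; 10.1%]. Section 10.4 does not name the arm. Section 10.2 attributes the same figures to that trial's control group, and section 5.8 says the control group for this study comes from that trial.

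Section 10.2 describes the comparison in general terms: "The confidence interval is then to be compared with the confidence interval of the results found by" the reference trial. It assumes a true rate of 1.2% for the test dressing, "as we expect it to be as good as the intervention group" of that trial, and states that "50 completing subjects will give a power of more than 80% to show an upper 95% confidence limit of 7.2% or less". It adds that the precision "is evaluated to be sufficient to draw comparative conclusions between the rate of hospital-acquired sacral pressure injuries found in the suggested observational investigation" and published rates. Section 10.4 adopts neither the 7.2% limit nor the 1.2% expectation.

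On method, section 10.1 says: "By use of an exact test in the Binomial distribution a 95% confidence interval will be estimated for the proportion". Section 10.3 says: "A two-sided significance level of 5% will be applied". The endpoint is exploratory (5.4). Section 5.5 gives its purpose as examining how well the dressing helps to prevent pressure injuries.

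**The concern.** A control-group rate is what one would expect from a dressing that adds nothing to usual care. A rule that is met by resembling that rate therefore cannot support the performance question in 5.5, whatever meaning is given to comparable. Because no meaning is fixed in advance, the same data can pass or fail according to a reading chosen after the result is known. Zero events in 50, the best possible result, passes two natural readings and fails a third.

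Section 10.2 might be expected to fill the gap with its power statement and its claim that comparative conclusions can be drawn. If neither holds against the 5.3% comparator, the report would have a criterion it can declare met but no inference in the direction of benefit to go with it.

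**Working it through.** **Inputs.** Reference rate 5.3% [2.3%; 10.1%], control group (10.2, 10.4). Assumed true rate 1.2%, planning limit 7.2%, 50 completers, 67 enrolled (10.2). Exact binomial interval (10.1, 10.2), two-sided 5% (10.3). Section 10.1 names both the ITT population and completed subjects for this endpoint, so 50 and 67 are both shown.

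**Step 1: the plan's own power figure.** With 0 events the exact two-sided upper limit is 1 − 0.025^(1/n). At n = 50 this is 7.11%. With 1 event it is the 97.5% quantile of Beta(2, 49), which is 10.65%. So a limit of 7.2% or less is met only with 0 events.

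- P(0 events) at 1.2% = 0.988^50 = 0.547, against the stated value of more than 80%.
- P(0 or 1 event) = 0.547 + 50 × 0.012 × 0.988^49 = 0.547 + 0.332 = 0.879. A figure above 80% at n = 50 needs 1 event to be allowed, but its upper limit of 10.65% exceeds both 7.2% and 10.1%.
- At n = 67 still only 0 events qualify, and the power is 44.5%.
- A one-sided 95% limit does not rescue the figure at n = 50 (5.8% for 0 events, 9.1% for 1). It would give 80.8% at n = 67, but 10.2 states 50 completers and 10.3 a two-sided level.
- At least 80% power is first reached at n = 98, where 2 events are allowed (88.6%).

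**Step 2: what passes under each reading of comparable.** The readings are assumptions, since the plan supplies none. Probability of passing at n = 50:

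| Reading | Events that pass | True 1.2% | 5.3% | 10% | 15% |
|---|---|---|---|---|---|
| Estimate inside 2.3% to 10.1% | 2–5 | 12% | 70% | 58% | 22% |
| Interval contains 5.3% | 0–6 | >99.9% | 98% | 77% | 36% |
| Intervals overlap (permissive bound) | 0–10 | >99.9% | >99.9% | 99% | 88% |

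The boundaries at n = 50 are:
- Estimate inside: 1/50 = 2% and 6/50 = 12% fall outside; 2/50 = 4% and 5/50 = 10% fall inside.
- Contains 5.3%: the lower limit is 4.53% for 6 events and 5.82% for 7.
- Overlap: the lower limit is 10.03% for 10 events and 11.53% for 11.

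These sets are unchanged when the three reference figures vary within their rounding. At n = 67, estimate inside gives 2–6 (19% at a true 1.2%, 81% at 5.3%) and overlap gives 0–12. The contains-5.3% set is 0–7 or 0–8 depending on rounding.

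**Step 3: the best case for benefit.** The upper limit for 0 events is 1 − 0.025^(1/50) = 7.11% at n = 50 and 1 − 0.025^(1/67) = 5.36% at n = 67. Both exceed 5.35%, the top of the range that rounds to 5.3%. The other direction is open: 7 events in 50 would show a rate above 5.3% (lower limit 5.82%).

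At n = 68, 0 events gives 5.28%, which turns on how 5.3% was rounded. At n = 69 it gives 5.21%, below any rate that rounds to 5.3%, with probability 0.988^69 = 0.435 at a true 1.2%.

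**The case against.** The strongest reply is that this is an exploratory endpoint in a study whose aim and primary objective are safety. Section 10.1 plans an estimate with an interval and no hypothesis test, and nowhere do the documents say that meeting 10.4 would demonstrate prevention. That limits the consequence: no stopping rule and no primary safety conclusion rests on the rule. It does not remove a mandatory requirement placed under a pass/fail heading, and 10.2 itself claims that comparative conclusions can be drawn.

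A reader might infer that the plan would call 10 injuries in 50 (20%, about 3.8 times 5.3%) a success. The documents do not support that. It follows only from the overlap reading, which drops the proportion that 10.4 names alongside the interval, and 10 events passes it narrowly (10.03% against 10.1%). It is a permissive bound, not the plan's rule.

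A reader might also infer that the study can support no comparison with any published rate. That is not shown. The synopsis refers to global, European and Scandinavian rates, and the documents do not give them. The arithmetic covers only 5.3%.

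Finally, the analysed number might exceed 67. Section 6.5 provides for replacement if more than 17 subjects drop out, although it also says withdrawn subjects will not be replaced. At the plan's 30% dropout, 50 completers need 50/0.70 = 71.4, so 72 enrolled. If all 72 were analysed, 0 events would give an upper limit of 4.99%. This route is open but not assured.

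**Conclusion.** The point stands, as a fault in a stated rule that should be fixed. The only pass/fail criterion requires similarity to a control-group rate, without margin or direction, so meeting it cannot support the performance that 5.5 sets out to examine. A dressing no better than the control rate passes the contains-5.3% and overlap readings with probability 98% or more. The estimate-inside reading fails 0 or 1 event and passes a dressing at the expected 1.2% only 12% of the time.

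At 50 to 67 analysed subjects and the two-sided 5% level, a rate below the 5.3% control estimate cannot be shown. The claim in 10.2 that comparative conclusions can be drawn therefore fails in the direction of benefit against this comparator. This could change at 69 or more analysed subjects. The stated power of more than 80% is wrong under the plan's own inputs: it is 54.7%. Meeting the 7.2% limit would not show benefit either, because 7.2% lies above 5.3%.

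The power and limit results rest on exact two-sided binomial intervals as specified in the plan. The pass probabilities rest also on the assumed readings of comparable.

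**What to change.** 1. **Section 10.4.** Replace the criterion with: *No pass/fail criterion is set for the exploratory endpoint. The proportion is reported with its exact two-sided 95% CI and compared descriptively with published rates; similarity to the control-group rate will not be taken as evidence of prevention.* Add the word *descriptively* to the comparison statements in the synopsis, 3.1 and 10.2, so that the promised comparison is kept and the sections agree.
2. **Section 10.2, power.** Restate it as about 55% at n = 50. Alternatively, delete it and give the precision: upper limits of 7.1%, 10.6% and 13.7% for 0, 1 and 2 events at n = 50, and 5.4%, 8.0% and 10.4% at n = 67.
3. **Section 10.2, comparative conclusions.** Limit the sentence by stating that at 50 to 67 subjects a rate below the 5.3% control estimate cannot be shown.

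The change is to wording and needs no new data. Section 12 requires a signed amendment and a change-log entry, with ethics committee notification if the change is significant. Section 10.6 requires deviations from the statistical plan to be documented in the report. The document is dated 28-03-2023 and planned last completion was 8 December 2022 (approximate); the documents do not say whether data had been reviewed. If they had, keep the present 10.4 sentence on record and report the change as post hoc. The downside is a weaker announced claim.

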10.5. Interim analysis

There will be no interim analysis and therefore no reason to terminate the investigation based on statistical considerations.

10.6. Statistical reason for termination of investigation

Any deviations from the statistical plan will be documented in the clinical investigation report - CIR.

11. Data management

11.1. Data collection and data management

11.1.1. Data Collection in the clinical investigation

Data management and the final statistical analyses of all measurements described in this protocol are carried out by the Medical Affairs, Coloplast A/S.

Data will be collected through an electronic data capturing (EDC) system on electronic Case Report Form (eCRF), internet-based case report form. This system will be used to record all subject information collected in the investigation for secure data tracking and centralised data monitoring ("remote monitoring") done by monitors, as defined in the monitoring plan.

The EDC Rave system is used. The system is designed to be compliant with the FDA requirements of 21 CFR part 11. It is a validated data management system. The system has full audit trail and electronic signature. The data management system has restricted role-based access control allowing only qualified and trained personnel to enter the system.

The Principal Investigator or delegate will enter data in a part of the system referred to as the eCRF.

The sponsor will be responsible for training the investigator or delegate, in completion of the eCRF.

Principal Investigator, or delegate will perform primary data collection directly into the eCRF or drawn from source-document (medical records) reviews. The eCRF will be completed on a continuous basis starting from the point of enrolling the subject to final follow up.

The eCRF will be completed by the investigator, or delegate, who have signed the Site Personnel Signature and Delegation List and Clinical Investigation Training Log. It will be the responsibility of the Principal Investigator to ensure that all measurements and observations are correctly noted in the eCRF.

All assessments and observations throughout the investigation for each subject must be carefully recorded in an eCRF during the visit or immediately after. The eCRF makes it possible to enter data right away when they are obtained. This is the preferred way of collecting data.

In the unforeseen situation, where clinical investigation personnel cannot establish connection to the EDC system a paper CRF (pCRF) has been printed and supplied by sponsor. As soon as connection to the eCRF is established data should be entered.

Adverse events should be registered following the timelines described in the Adverse Event section.

The investigator will keep a separate list of the subjects' ID numbers, names, and addresses in a locked room/cabinet. Only data referred to in this clinical investigation plan will be recorded in the CRFs.

11.1.2. Database Management, Queries and Quality Control

The data management system has restricted role-based access control. The Principal Investigator or delegate must be trained in the system prior to getting access. The training is web-based and must be completed before access to the investigation is granted. Training will be documented in the data management system. Only the Principal Investigator, or delegate, will be authorised to enter data in the eCRF.

The monitor, using his/her personal login information shall verify all critical data points against the source documents and issue electronic queries for the authorised clinical site personnel to respond, as defined in the monitoring plan.

The Principal Investigator, using his/her personal login information shall sign each eCRF.

Automated, real time access to the data enable control on investigation compliance and safety assessments.

A critical quality control will be performed by the sponsor's data management team and queries issued where needed. Such queries will be reviewed by the monitor and must be resolved by the site personnel.

At the end of the investigation a formal data review meeting will be performed before the database will be locked.

A full audit trail ensures, that each user's (site personnel, monitor, sponsor, data manager) access to and actions in the system is tracked.

The Data Management Procedures are further described in the Data Management SOPs.

11.2. Remote monitoring

Remote (source data verification) and/or centralized (data review) monitoring is carried out by sponsor personnel or representatives (e.g., data management personnel, statisticians, or clinical monitors) at a location other than the site(s) at which the clinical investigation is being conducted (evaluation without visiting the investigation site). Remote monitoring processes can provide many of the capabilities of on-site monitoring as well as additional capabilities.

In addition to onsite monitoring visits, remote monitoring of the data entered in the e-CRF system could be used to achieve the following:

- Conduct activities such as: standard checks of range, consistency, and completeness of data and checks for unusual distribution of data, such as too little variance)
- Special attention will be given in case of frequent data anomalies or errors, protocol deviations or excessive dropouts.
- Augment on-site monitoring by performing monitoring activities that can only be accomplished using centralized processes (e.g., statistical analyses to identify data trends not easily detected by on-site monitoring)
- Monitor data quality through routine review of submitted data in real-time to identify missing data, inconsistent data, data outliers, and potential protocol deviations that may be indicative of systemic and/or significant errors in data collection and reporting at the site
- Verify source data remotely, provided that both source data and CRFs can be accessed remotely
- Conduct aggregate statistical analyses of investigational data to identify subject data that are outliers relative to others and to evaluate individual subject data for plausibility and completeness
- Conduct analyses of site characteristics, performance metrics (e.g., high screen failure rates, high frequency of eligibility deviations, and delays in reporting data), and clinical data to identify early on corrective actions needed for characteristics correlated with poor performance or noncompliance

11.3. Data retention

The Investigator file must be archived for a minimum period of 10 years after the final clinical investigation report has been signed.

12. Amendments to the Clinical Investigation Plan

No changes in the clinical investigation procedures shall be affected without mutual agreement between the Principal Investigator and the sponsor. The agreement of the changes must be documented by signing the corresponding clinical investigation plan amendments and registered in the Change Log.

All significant changes require notification to the EC. Substantial changes may require approval from the EC prior to implementation. (Example of significant change: Changes of inclusion criteria, end points or assessment methods).

13. Deviations from the Clinical Investigation Plan

Deviations to the Clinical Investigation Plan occurs when the activities during the clinical investigation do not comply with the EC approved investigation plan.

A minor deviation is defined as those that don't increase risk or decrease benefit or don't have a significant effect on the subject's rights, safety, or welfare; and/or on the integrity of the data. If a deviation increases risk or decreases benefit and/or has a significant effect on the subject's rights, safety, or welfare and/or has a significant effect on the integrity of the data it is defined as a major deviation and the Investigator must inform the monitor immediately, and the Monitor will report and inform the Clinical Manager or designee immediately.

The investigator is not allowed to deviate from the Clinical Investigation Plan unless, under emergency circumstances or to protect the rights, safety, and welfare of the subject(s).

For the purposes of this investigation, any variance from the protocol is considered a deviation and is to be reported.

The Clinical investigation personnel will complete a deviation eCRF form for all data-related deviations and all deviations that are not related to the data (for example, an untrained nurse performing investigation procedures) are reported by the monitor in the Site Report – Periodic Monitoring and actions are addressed to the Investigator for completion.

If any deviations to the investigation plan are detected during the monitoring visit, the Monitor shall ensure the site reports all deviations in the eCRF or on the Deviation log in the Investigator File. Additionally, the monitor must report any deviation noted during the visit in the Periodic Monitoring Report.

Monitor will align with data management in each investigation, how data management will be informed about all deviations.

The following information about the deviation will be collected:

- Date the deviation took place.
- State what the deviation is related to.
- Does the deviation affect data integrity?
- Does the deviation affect the subject's safety?
- Clear and concise description of the event.
- Corrective action taken.

14. Device Accountability

All access to the investigational devices used in the clinical investigation is controlled by storage procedures and device accountability logs as described below. The investigational devices must only be used in this clinical investigation and only according to the CIP.

Sponsor keeps a device accountability log that states the physical location of all investigational devices.

The PI or an authorized designee keeps records documenting the receipt, use and return and disposal of the investigational devices, which includes:

- Date of receipt.
- Identification of each investigational device (batch no./serial no./unique code).
- The expire date, if applicable.
- The date(s) of use.

- Subject identification.
- The date on which the investigational device was returned/explanted from the subject, if applicable.
- The date of return unused, expired or malfunctioning investigational devices, if applicable.

15. Statement of compliance

The clinical investigation is conducted in accordance with:

- Ethical principles that have their origin in the Declaration of Helsinki, 1964, Last amended at the 59th WMA General Assembly, Brazil, October 2013.
- MDD 93/42/EEC as amended by Directive 2007/47/EC (commonly known as the Medical Device Directive).
- MDR (EU) 2017/745.
- ISO 14155:2020 "Clinical Investigation of medical devices for human subjects – Good clinical practices".
- Any applicable regional or national regulations will be specified in the country specific CIP.

